Title: The Effectiveness of participation-focused interventions on body functions of youth with physical disabilities: An Interrupted Time Series Design

Data of submission: September 27, 2016

Data of approval for funding: March 23, 2017

Date of approval by Ethics board: May 29, 2017

Potential Impact

Participation of youth with physical disabilities in community activities is restricted¹, which is associate with poor health outcomes and undesired development targetories². Traditional therapies for this population focus primarily on remediation of impaired body functions (e.g., muscle tone, joint mobility, balance) in order to reduce activity limitations and participation restrictions. However, activity-based goal-directed interventions that are client-centered and implemented in the youth's natural environment are currently considered recommended practice to improve daily activities³. It is unclear; however, whether interventions targeting *activity and participation* **also** result in improvement of body functions and participation - both key rehabilitation outcomes and meaningful outcomes for youth and their families. While research in exercise programs suggest that therapist-prescribed exercise programs result in physical gains (e.g., postural control)⁴, the impact of participation in a chosen and meaningful, real-life activity (e.g., sledge hockey) on a range of body functions (i.e., motor, cognitive and affective) underlining the specific chosen activity has not been established. Moreover, effective methods for testing complex individual-based interventions and outcomes that are highly applicable to practice are lacking.

This study aims to better understand the benefits resulting from intervention strategies that improve participation. It thereby tackles one of the pressing knowledge gaps in the field of pediatric rehabilitation^{3b} and one of the urgent research priorities identified by both parents⁵ and clinicians⁶. To illustrate, in a worldwide survey of rehabilitation experts, social participation in leisure and recreational activities as well as movement-related components were ranked as the most relevant areas of functioning across all elements of the International Classification of Functioning Disability and Health (ICF)⁶. Aligned with this priority, this proposed project addresses outcomes at two key levels of the ICF, i.e., participation and body functions, with a single intervention strategy. These outcomes have not only been consistently identified as significant areas of restriction among children and youth with physical disabilities^{1, 7} but are also known to worsen with age⁸, and further complicating the challenging transition to adulthood⁹. Youth with disabilities utilize healthcare services 5 times more than the typical adolescent population¹⁰. This, therefore, highlights the need to find better and more efficient methods of delivering healthcare services. It also emphasizes the importance of focusing on this developmental stage, i.e., youth, during which life-long habits can be established through positive experiences and opportunities for participation, capacity building and empowerment⁹.

Interrupted Time Series design – a rigorous approach for studying complex interventions and outcomes

Given the complexity and highly subjective nature of the outcome of participation, particularly when occurring in the community¹¹, selecting pragmatic individual-based approaches that reflect and account for real-world clinical settings (e.g., variability of participants, their participation preferences/choices and their environmental characteristics) is critical¹². **This pilot study** will therefore employ a replicated individual-based multi-baseline experimental design across youth, termed Interrupted Time Series (ITS)¹³. In this design, the time-point in which the intervention is introduced for each youth is varied, and each youth serves as a unit of analysis and acts as its own control. By varying the baseline lengths across participants, extraneous variables are controlled for, which in turn strengthens the internal validity of the study allowing us to conclude with greater confidence that change in participation levels and body functions is due solely to the intervention. To further increase internal validity and to minimize potential bias, each youth is randomly assigned to the order (timing) of the intervention.

Embedded in Comparative Effectiveness Research (CER)¹² and in ITS designs¹⁴ we aim to achieve a broad and diverse sample of youth, as this provides an opportunity to replicate the intervention effect across different circumstances/environmental characteristics/community settings and, consequently, further supports the generalizability of results. ITS design is particularly relevant when targeting children with physical disabilities (e.g., CP) in which the variability in functioning is large¹⁵. It allows for heterogeneity within the studied sample and accommodates for complex cases, which is beneficial and meaningful in rehabilitation, as opposed to traditional Randomized Controlled Trials that employs strict exclusion criteria limiting the applicability of the findings to the clinical setting/reality. Furthermore, having a diverse sample allows for a better understanding of for whom and under what conditions the intervention is most and least effective – an important element of CER that can better inform clinical decision-making.

To systematically evaluate the overall treatment effect of aggregated single individual intervention effects, we proposed an innovative statistical solution that involves a combination of segmented regression¹⁶ and mixed-effects Hierarchical Linear Modeling (HLM) – a technique found effective in a recent intervention study that was funded by CIHR and led by [name] (NPA), targeting the outcome of participation. Notably, such an analytical approach can detect a change in outcomes that is clinically significant (e.g., the extent to which the intervention can result in a 2-point change on the activity performance scale of the Canadian Occupational Performance Measure) rather than estimate a general effect size and, therefore, provides meaningful evidence that can directly/better inform clinical decision-making. **In summary, the proposed ITS design, accounting for intra-individual changes and involving innovative analytical solutions, is practical as it offers a rigorous alternative for efficacy studies and is considered most appropriate for studying participation-based interventions¹⁷.**

Anticipated impact for youth, clinicians and policy makers

To date, only a few small-scale studies among children with physical disabilities have demonstrated that participating in mainstream, real-life, community-based activities/programs such as ice-skating and yoga leads to improvement of motor functions (i.e., balance, flexibility, posture, strength)¹⁸. Moreover, these studies do not document the impact of the above-mentioned activities on other body functions (e.g. self-esteem, attention span) and/or on participation outcomes itself (e.g., social interactions, developing friendships)¹⁸. Concerted effort is therefore needed to evaluate the impact of interventions that are enjoyable, socially engaging, guided by

youth preferences and occur within their natural environment across a range of body functions. Such interventions hold promise as they are perceived as motivating to the youth¹⁹ and can thus promote adherence to healthcare treatment and sustainability following their completion²⁰.

This early study in the area will build knowledge that can guide clinicians, families and policy-makers in appraising the benefits of participation-based therapies on improving functional capacities as well as actual performance of meaningful life activities. Findings can also encourage rehabilitation practitioners to consider additional intervention options for improving outcomes at the level of body function rather than solely focusing change on remediation of impairment. Increasing therapeutic options can contribute to customized care that is more responsive to the needs, resources and preferences of the youth and families. Furthermore, describing the multiple benefits potentially generated by **one single** intervention can facilitate the development of efficient youth-engaging therapies, therefore contributing to the improvement of the provision of pediatric rehabilitation services. Finally, in-line with CER, our study proposes a flexible client-centered intervention protocol using the ITS design which builds on a *non-concurrency* principle – it does not require all participants to start the intervention simultaneously, which is a more accurate reflection of ‘real life’ practice.

Scientific Merit

With CIHR funding, we have established the effectiveness of the PREP intervention, i.e., Pathways and Resources for Engagement and Participation, in promoting youth participation^{21 22}. The PREP²³ is an environment-based approach aimed at improving participation in community activities by removing environmental barriers and coaching youth/parents. Using elements of the PREP, the **goals** of this study are to: 1) generate preliminary data of the effectiveness of youth engagement in a 6-week community-based activity program (e.g., sledge hockey) on underlying body functions (e.g., movement, attention, mood) and activity performance and 2) examine the feasibility and applicability of the proposed design and intervention protocol. Specifically, **we aim**: 1) to gather pilot data and explore the effectiveness of the intervention on change in 3 relevant body functions: **motor**, **cognitive** and **affective** and to systematically replicate this effect across 8 youth with physical disabilities; 2) to estimate the optimal length and intensity of the intervention/community program, the relevancy of the proposed assessment kit in effectively capturing change in the three body functions and the feasibility of identifying and repeatedly collecting data on the specific 3 body functions underpinning each chosen activity; and 3) to examine the extent to which the outcomes vary within and across participants in order to estimate sample size required for a larger study. **We anticipate**: 1) a significant positive change in at least 2 of the 3 body functions within 6 of the 8 participants (75%) following the intervention; 2) that the proposed intervention protocol and study design will be feasible and applicable in at least in 6 out of the 8 cases; 3) obtaining a better understanding of whom and under what conditions/circumstances the intervention is most and least effective.

Methods

Eight youth, aged 15 to 24 years as defined by the United Nations²⁴, will be purposefully selected from a pool of clients receiving services in two major rehabilitation centers in Greater Montréal from both the Anglophone and Francophone communities. Participants will be included if they have 1) a physical disability (e.g., cerebral palsy, spina bifida, musculoskeletal disorders, muscular dystrophy); 2) restricted mobility, such as an inability to navigate all surfaces and stairs independently and safely without the use of aids, physical assistance or external support. Multiple diagnostic categories will be used, as research among children and

youth with physical disabilities shows that participation does not vary across specific diagnostic categories²⁵. Moreover, such an inclusive approach reflects real-world clinical practice, where variability in functioning level is evident across patients, making the findings relevant to various conditions and, hence, highly applicable to practice. Youth who are recovering within the first year following a severe brain injury or an orthopedic surgery will be excluded, as their functional capacities are less likely to be stable.

Intervention and Procedure

Based on the 5-Ms or steps of the PREP approach²³ found effective in improving youth participation²¹⁻²² (i.e., **M**ake goals; **M**ap out a plan; **M**ake it happen; **M**easure the process and outcomes; **M**ove forward), an Occupational Therapist (OT) will meet individually with each youth/family in their home. The intervention includes up to 12 hours of therapy time; the first 2-hour session will encompass setting a new participation goal or activity that the youth would like to engage in yet finds difficult. The Canadian Occupational Performance Measure (COPM)²⁶ will be used to identify participation issues from the youth's perspective. This process will lead to pinpointing a specific community-based activity that the youth will engage in for a period of 6 weeks (e.g., ice skating, sledge hockey, boccia, yoga). Together with the youth and family (as needed), this activity will be analyzed using the Task Analysis approach²⁷ to identify the specific underlying body functions that are required by the activity and that the youth finds most difficult and wants to improve on (e.g., posture, balance, strength, self-efficacy, attention). Three appropriate measures to monitor each corresponding function (motor, cognitive, affective) will be selected from a pool of 5 relevant scales. These 5 assessments, recommended by Majnemer²⁸ and guided by the ICF linking rules²⁹ include: the Spinal Alignment and Range of Motion Measure (SAROMM), the Trunk Impairment Scale (TIS), the Functional Reach Test (FRT), the Jamar dynamometer for evaluating **motor-related components**, and the Behavioral Assessment System for Children (BASC-2) to assess **cognitive and affective functions**. To illustrate, if task analysis of sledge hockey indicates that trunk control or range of motion of upper extremity is required for activity engagement, TIS or the SAROMM will be used, respectively.

[figure not shown]
Two weeks following the first session, the baseline period will start and the identified body functions will be repeatedly measured every week, as will the performance of the chosen activity by an assessor, independent of the intervention. During this baseline period, the OT will use the 5-Ms of the PREP protocol to search for the appropriate community program, to identify and remove potential environmental barriers for participation in that activity (e.g., accessibility, equipment) and to educate program instructors regarding the specific needs and abilities of the youth. This will set the stage for enrolment and engagement of the youth in a structured program offered at least once a week. Using a structured form, the therapist will document information about the program and any specific circumstances involved. The OT will also serve as a consultant and perform site visits during this 6-week program to ensure youth engagement. Based on our experience employing the PREP intervention, a 6-week duration is sufficient to observe change in activity performance²¹⁻²². This timeframe also permits the building of motor functions^{18a, 30} while considering aspects of program management and adherence that can potentially reduce dropout rates²⁰.

Study design

Two blocks of an 18-week individual-based interrupted time series design with multiple baselines across 4 participants will be employed (Figure 1). To increase internal validity, each of the 4 participants will be randomly assigned to 4 different lengths of baseline: 2, 4, 6 and 8

weeks. A 6-week intervention will then be implemented for each participant. Four outcome measures will be monitored weekly throughout the three phases of the study: baseline, intervention and follow up (week 16 and 18). Figure 1 illustrates the ITS design across 4 participants; it will be replicated 2 times resulting in the examination of 8 participants. Three body functions: motor, cognitive and affective will be measured weekly, resulting in 3 individual trajectories of change – each based on 18 equally-spaced data points. The performance of each activity will also be monitored weekly using the performance scale of the COPM – a 10-point scale that is valid, reliable and sensitive-to-change²⁶. This will result in 24 trajectories of change in body function (8 participants X 3 body functions) and 8 additional trajectories illustrating change in performance in the actual activity (8 participants X 1 activity). Thus, a total of **32 trajectories**, 4 per participant, representing 8 profiles of change will be plotted and analyzed. A combination of 8 cases measured on 18 occasions allows us to estimate the overall effectiveness of the intervention (Aim 1) as well as to determine aspects of feasibility and applicability (e.g., duration of intervention, optimal number and intervals of data points, etc) of this design (Aim 2) and assist in calculating a sample size for a larger clinical trial (Aim 3)³¹.

Figure 1 - Study Design

A kit of outcome measures to assess body functions

A kit of 5 measures will be available to assess motor, cognitive and affective body functions over time. Based on the task analysis, the therapist and youth will select one aspect of each body function (3 total) required to complete the chosen activity, while considering the existing impairments and strengths of the youth; 4 options of assessments will be available for the **motor** aspect and a single tool for both **cognitive and affective** functions with multiple sub-scales for

each function. The therapist will match the assessment including specific sub-scales to the identified body functions by drawing on the ICF linking rules²⁹. If more than one component of a specific body function is identified, the most impaired one will be selected by the youth.

Assessors, independent of the intervention, will administer the assessments every week at the youth's home (30-60 min). They will be blinded to the time point in which the intervention begins and to the actual chosen activity/program.

To measure the **affective** (e.g., anxiety, social stress, self-esteem), and **cognitive** (e.g., attention problems, learning problems) aspects of body function, the self-report form or parent form of the **BASC-2** will be used, depending on the youth's ability. The **BASC-2**, completed in 15-30 minutes, is a valid and reliable 4-point scale for evaluating behavior and self-perception of children; such as externalizing and internalizing problems, behavioral symptoms and adaptive skills/personal adjustment³².

To measure **motor-related** body functions, four measures can be used: the **SAROMM**, the **TIS**, the **FRT** and the **Jamar dynamometer**. The **SAROMM** is administered by a trained rater and requires 15 to 30 minutes to complete; it measures active/passive range of motion of lower and upper extremities as well as spinal movements using a 5-point scale. The **SAROMM** has demonstrated good inter-rater and test-retest reliability (>.80) as well as sufficient construct validity³³. The **TIS** assesses trunk control and includes 3 sub-scales; static sitting balance, dynamic sitting balance and coordination, and is administered in less than 20 minutes. It contains 17 items rated on a 2-, 3- or 4-point scale. Total score ranges from 0 (low performance) to 23 (high performance). The **TIS** was found to be reliable and valid among youth with CP³⁴. The **FRT** assesses the maximum distance in inches the participant can reach forward while standing/sitting in a fixed position. It is a reliable, valid and responsive tool³⁵ and takes 5 minutes to administer. The **Jamar dynamometer** measures grip strength; scores range from 0 to 200 pounds of force and normative data has been established for youth³⁶.

All scores will be converted to z-scores based on available data of standard deviations and mean scores of this population; this will allow for comparison across trajectories and the examination of the overall effect of the intervention statistically (Aim 1).

Anticipated output #1: A significant change in at least 2 of the 3 body functions will be observed in 6 of the 8 participants (75%) following the intervention.

Two evaluators, both experts in analyzing multi baseline single-system replicated data, will analyze the data independently using a visual inspection approach following the guidelines of Hawkins et al³⁷ to detect changes in body function over time. To minimize bias, experts will be blinded to the time point in which the intervention was introduced. Specifically, experts will indicate if/when a change in body function and activity performance has occurred, and the direction of that change (increase/decrease). Consensus between experts will be reached via discussion and consultation with a third expert. The number of trajectories indicating a significant positive change in outcomes will be counted.

To complement visual inspection, the overall effect of the intervention will be statistically estimated within and across participants. Specifically, we will use an innovative analytical technique that combines segmented regression¹⁶ and mixed-effects HLM that was found useful in evaluating replicated individual-based ITS designs³⁸. This meta-analysis of treatment effect uses a small-sample bias-correction method and accounts for autocorrelation and individual variance. Moreover, it can estimate the extent to which a change in outcomes (youth's performance and functions) is clinically significant rather than solely reporting the effect size, as is common in traditional analytical approaches.

Anticipated output # 2: Proposed intervention protocol and study design will be feasible and applicable in at least 6 out of the 8 cases.

Information about the feasibility and applicability of the proposed approach in terms of length and duration of the program, length of baselines, number of completed data points/repeated measures, relevancy of assessments in capturing change in performance and body function will be recorded using a structured form/checklist. This form/checklist draws on the recommendations of Tickle-Degnen³⁹ for examining feasibility elements. Two reviewers, independent of the study, will autonomously evaluate these elements for each case and any discrepancies will be resolved through a discussion until consensus is reached.

Anticipated output # 3: To better understand to whom and under what conditions the intervention is most and least effective.

The two experts will independently conduct a systematic classification process¹⁷. Each expert will detect similarities and differences in patterns of change within each case using Hawkins et al.³⁷ guidelines. In this process, cases will be clustered based on aspects of change that reflect the extent of the intervention effect. Examples include: number of replicated effects across body function and level and trend of change. Once an agreement is reached and clusters are formed, group members/cases will be described in terms of age, sex, income, the characteristics of the community-based activity programs, the length, intensity and activity type (based on the therapist's structured form) as well as functional issues (based on assessment of body functions). Such an analysis will allow us to identify the profiles of youth for whom the treatment is more effective and less effective as well as the conditions under which the change is observed or partially observed. Furthermore, this information, analyzed with the input of stakeholders, can inform the design of a larger clinical trial testing this intervention.

Potential Challenges and ways to overcome them

Like in many 'real-life' studies, youth may wish to continue participating in the chosen program beyond the 6-week period or decide to engage in an additional activity simultaneously. Such occurrences will be documented by the therapist and will be incorporated into the analysis. This information will assist in identifying specific circumstances that may influence the results (Anticipated output #3). It is plausible that specific programs prioritized by youth will not be available in their community at a certain time (e.g., seasonal sports). A discussion will take place to identify ways to engage in a similar activity while adhering to the area of interest that was expressed. The therapist will document this process. Additionally, some youth might prefer to start the intervention before completing the assigned baseline period (either 2, 4, 5, or 8 weeks). Through a discussion with the youth and their family, the reason for employing such procedure will be described. Furthermore, during the baseline period, youth are allowed to continue and receiving any ongoing rehabilitation services and this will not be affected by such a delay.

Research team

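### Aim 2 promises an optimal programme length and intensity, but planned length has one level and intensity is not assigned, so the study can assess only whether 6 weeks is feasible and long enough to see change

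*Combined protocol and SAP*

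**What the plan says.** Under Scientific Merit, the first part of Aim 2 is "to estimate the optimal length and intensity of the intervention/community program". Study design returns to it, saying that 8 cases on 18 occasions will inform aspects of feasibility and applicability, with the examples "duration of intervention, optimal number and intervals of data points, etc".

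The design features that bear on this are:

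- **Length.** Study design: "A 6-week intervention will then be implemented for each participant".
- **Randomisation.** Study design: "each of the 4 participants will be randomly assigned to 4 different lengths of baseline: 2, 4, 6 and 8" weeks. Nothing else is randomised.
- **Programme frequency.** Intervention and Procedure asks for "a structured program offered at least once a week".
- **Therapist contact.** Intervention and Procedure: "The intervention includes up to 12 hours of therapy time".
- **Sample.** Two blocks of four: "it will be replicated 2 times resulting in the examination of 8 participants".

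Four parts of the plan touch length or intensity afterwards:

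- Under Anticipated output #2, two independent reviewers complete a checklist that includes programme length, against a 6-of-8 feasibility criterion.
- Under Anticipated output #1, blinded experts judge from each trajectory whether and when change occurred.
- Under Anticipated output #3, length and intensity are among the descriptors of clusters already formed by response.
- Under Engagement and Partnership, the consultation committee is asked at its first meeting for its view on programme duration.

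**The concern.** To call a length or an intensity optimal, the study has to observe what happens at other lengths or intensities. Here length is held constant by design. The factor that does vary by design, baseline length, determines when the programme starts and not how long it lasts. Intensity is left to the activity the youth chooses and to what the therapist delivers. The activity also drives which functions are followed and which instrument or sub-scale measures them.

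The stake is the larger trial that this pilot is meant to inform. A length or intensity reported against Aim 2 as written could be carried forward as though alternatives had been tested. Improvement over 6 weeks would show only that 6 weeks was enough to see change, which Intervention and Procedure already asserts for activity performance on the strength of past experience.

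**Working it through.** The plan gives no power, precision or sample-size figure for Aim 2, so there is nothing to reproduce. Its counts agree: 2 × 4 = 8 youth, and 8 × 3 + 8 × 1 = 32 trajectories.

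**Planned length, between youth.** Let L be planned length, with L = 6 for all 8 youth. In a model with an intercept and L, the L column is 6 times the intercept column, so the rank is 1 of 2. Adding randomised baseline length B = (2, 4, 6, 8, 2, 4, 6, 8) gives rank 2 of 3. The coefficient of L stays inestimable. More youth on the same schedule would not change this.

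**Length, within youth.** The 18-week window leaves 18 − B − 6 weeks after the programme: 10, 8, 6 and 4 weeks for baselines of 2, 4, 6 and 8. If measurement is weekly throughout, each trajectory can show when change starts and whether it levels off. The value at an intermediate week might stand in for the end of a shorter programme, on the assumption that the course up to that week would have been the same. It does not show whether gains would last after an earlier stop, or what a longer programme would add.

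**Intensity.** There is a floor (once a week) and a ceiling (12 therapy hours), with no levels between. If intensity were constant within an activity, it would add nothing once activity is in the model. With 8 different activities, the residual degrees of freedom after activity are 8 − 8 = 0; with 4 activities, 8 − 4 = 4. The documents do not say how many activities will be chosen, so these two cases are assumptions that show a range.

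**Intensity if it were unconfounded.** Assume one value per youth, a linear relation and a two-sided test at 0.05. None of these is in the plan.

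- Smallest significant correlation: r = t / √(t² + 6), with t = 2.447 on 6 df. This gives 2.447 / √(5.99 + 6) = 0.71.
- Simulated power with n = 8 (bivariate normal, 100,000 runs):

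| True r | Power |
|---|---|
| 0.5 | 25% |
| 0.7 | 55% |
| 0.8 | 75% |

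- 95% interval for an observed r of 0.5: tanh(atanh 0.5 ± 1.96/√5) = tanh(0.549 ± 0.877), or about −0.32 to 0.89.

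Even in this favourable case, 8 youth could not separate a useful intensity effect from none unless the relation was very strong.

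**The case against.** The best defence is that Aim 2 is a feasibility aim and that *estimate* there means *appraise*. The same verb also governs the relevance of the assessment kit and the feasibility of repeated data collection, neither of which is a parameter. The parent goal concerns feasibility and applicability, Study design files duration under that label, and Anticipated output #2 turns it into a checklist. This largely stands as an account of what will be done. It does not remove the word *optimal* from the aim, and the checklist, profiles and committee opinion cannot supply an optimum.

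A reader might infer three stronger things that the documents do not support:

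- *That the plan will compute an optimum from a confounded comparison.* No planned analysis compares lengths or intensities. The risk lies in how results are reported against the aim.
- *That intensity varies only with the activity chosen and is fully confounded with it.* Therapy hours can differ between youth. Potential Challenges also allows for an added activity and for continuing past 6 weeks. Intensity and actual length can therefore vary in other ways, and youth may share an activity. This variation is self-selected, so it does not rescue the aim, but complete confounding is the worst case and not a stated fact.
- *That the study is silent on length.* The weekly trajectories and the experts' judgement of timing bear on whether 6 weeks is long enough to see change.

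It is also fair to say that this is an exploratory pilot and that no count or sample size in it changes as a result.

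**Conclusion.** The aim is wrong as written, within a limited scope. The study cannot estimate an optimal length: there is one planned level, and its effect across youth is not identifiable at any sample size. It cannot estimate an optimal intensity either, because no levels are defined or assigned, and whatever variation arises will be self-selected and mixed with activity, function and measure. The length conclusion needs only the planned fixed 6 weeks. The intensity conclusion rests on the absence of assignment, and the correlation figures are illustrations under stated assumptions.

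What the data can support is narrower and still useful: whether a 6-week programme is feasible, when change first appears, and whether it is still rising at the end. The other parts of Aim 2, on the assessment kit and on repeated data collection, are not affected by this point.

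**What to change.** 1. Restate the first part of Aim 2 as assessing the feasibility and adequacy of the 6-week programme, and state that no optimal length or intensity is estimated. Reword the mention of duration in Study design to match.
2. Use the weekly points and the experts' existing judgements. For each youth and outcome, report the programme week at which change is first detected and whether it is still rising or has levelled off by week 6. The experts are blinded to the start, so programme week is obtained afterwards by subtracting the weeks elapsed before the programme began. Note that each judgement rests on about six points in the intervention phase.
3. Summarise sessions attended and therapist hours descriptively. Confirm that the therapist's structured form records both, along with continuation and added activities.
4. Optional, for the question of measurement interval: refit using every second week and report the loss of precision. The caveat must be stated that the two youth with a 2-week baseline (one per block) would keep one baseline point, and that each intervention phase would keep three.

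The cost is a less ambitious aim and a small amount of extra analysis. No new outcome assessments are needed, and neither the intervention nor the sample size changes.
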